9.16 Sample processing and specimen management

Within the UCSF SCOPE infrastructure, initial sample processing is performed on peripheral blood and leukapheresis units. All samples at UCSF and UCLA are tracked through Laboratory Information Systems, such as LDMS, or in-house systems with sample storage inventories, multiple report formats, and Institutionally-managed data storage and back-up systems.

The SCOPE Program will use the AIDS Specimen Bank (ASB) for preserving and distributing study specimens. ASB provides an established infrastructure with expertise in specimen processing and storage. It has received >188,000 deposits and has distributed >192,000 specimen aliquots worldwide. Specimens are stored in ultra-low temperature freezers with back-up power systems, in which temperature is monitored by a programmable scanning alarm system wired into the university's telephone system.

10 EVALUATIONS BY VISIT

10.1 Overview

Participants will be consented by the Principal Investigator or the research team before any procedures take place.

Once a participant is identified as potentially eligible by review of screening criteria and is to be scheduled for a screening visit, a unique identifier (4-digit SCOPE ID) will be assigned. Once a SCOPE ID is assigned, it cannot be reassigned to another subject.

Subjects who satisfy all inclusion/exclusion criteria will be enrolled into the study, which is summarized in the Schedule of Events.

A brief medical history will be obtained at each visit. We will collect, analyze and report all available data related to any potentially immune-mediated medical conditions (PIMMCs, Appendix A) through week 86.

Blood collection will occur at all visits as per the Schedule of Events and will be timed to stay within Red Cross Guidelines (less than 480 mL every 8 weeks).

Given the expected age of our study population (most will likely be at least 50 years old) we expect many participants to have a number of chronic medical conditions, which might change over time. The interval between the screening visit and the first study vaccination will be limited to 60 days.

All subjects will be observed for adverse reactions for at least 30 minutes after administration of any of the final study product and at least 4 hours after administration of bNAbs.

Pregnancy and HIV transmission precautions will be discussed extensively throughout the study. For women of childbearing potential, pregnancy testing will be performed at a minimum as per the Schedule of Events and at other visits as needed per the discretion of PI/Co-I, and the results discussed at each visit. The need to prevent pregnancy will be discussed as needed throughout the study. The risk for transmitting HIV to others will be discussed in detail and at each visit during the treatment interruption phase (Stage 5). All study participants will be informed that virus rebound could happen at any time during the interruption, and that high-level viremia may occur even in the absence of symptoms. The risk that any virus rebound poses to sexual partners will be discussed. Methods to prevent HIV transmission to others will also be discussed. See Appendix B for risk mitigation strategies.

Study specific case report forms will be administered for data collection and clinical assessments as described in Sections 9.1-9.3.

10.2 Procedures: Staggered enrollment

Given limited clinical experience with some of the components of the combination regimen, subjects will be enrolled in a staggered fashion. Specifically, a pilot group of 3 individuals will start vaccinations four weeks before opening up the study to the others.

10.3 Screening and baseline evaluations

Screen: Prior to conducting any study-related activities, written informed consent and the Health Insurance Portability and Accountability Act (HIPAA) authorization must be signed and dated by the subject.

All participants are assigned a unique four-digit number. For those already enrolled in SCOPE, we will continue to use their existing number. New participants will be assigned a unique SCOPE number during screening. Once a SCOPE ID is assigned, it cannot be reassigned to another subject.

A medical history and physical examination will be performed. Participants will undergo an ophthalmologic examination between screen and prior to study entry.

Hematology, metabolic/chemistry and coagulation (PT/PTT) studies will be performed. Hepatitis B and C studies will be performed. Individuals with prior documentation Hepatitis B immunity will not require Hepatitis B testing. Individuals with prior documentation of negative Hepatitis C antibody and who lack new risk factors will not require retesting of Hepatitis C antibody although it may be repeated at the discretion of the PI.

A pregnancy test will be performed in women with child-bearing abilities.

Plasma HIV RNA levels and CD4+/CD8+ T cell counts will be measured.

A screening test to assess for phenotypic susceptibility to 10-1074 and VRC-07 (PhenoSense Neutralizing Antibody Assay) will be performed by Monogram Biosciences. Individuals who have previously measured phenotypic susceptibility to 10-1074 and VRC-07 do not need to have this test repeated if they have remained on suppressive ART (as outlined above), although it may be repeated at the discretion of the PI.

An electrocardiogram will be performed.

Screening evaluations should be completed within 60 days prior to study entry.

Baseline visit 1 (B1, week -4 to day -3): Plasma HIV RNA levels and CD4+/CD8+ T cell counts will be measured. Routine safety laboratory tests (hematology and chemistry laboratories) will be performed. Plasma and PBMCs will be collected and cryopreserved. Serum may be collected (see B2D0 below).

10.4 p24CE and IL-12 DNA vaccinations (Stage 1)

Entry /baseline visit 2 (B2 D0): The second baseline visit will occur.

Routine safety studies (hematology and chemistry laboratories) will be performed. Plasma HIV RNA levels and CD4+/CD8+ T cell counts will be measured.

Plasma and PBMCs will be collected and cryopreserved. Serum may be collected (must be collected on B2D0 or within 4 weeks prior).

A PAXgene specimen will be collected.

A urine pregnancy test will be performed and evaluated prior to vaccination (in females of childbearing potential). If the urine pregnancy test is positive, the positive result will be confirmed with a serum pregnancy test. If the serum pregnancy test is positive, all study interventions will be discontinued.

Subjects will initiate treatment. Study product (p24CE vaccine and IL12 DNA plasmids) will be administered by electroporation. Subjects will be observed for 30 minutes after vaccine administration to assess for immediate injection site reactions and adverse events.

Day 1: Subjects will be contacted by telephone to check on symptoms and overall response to the injections.

Week 1: This visit will take place 7 +/- 2 days from the date of the B2D0 visit. Routine safety studies will be performed. Plasma HIV RNA levels and CD4+/CD8+ T cell counts will be measured. Plasma and PBMCs will be collected and cryopreserved. A PAXgene specimen will be collected.

Week 4: Routine safety studies will be performed. Plasma HIV RNA levels and CD4+/CD8+ T cell counts will be measured.

A urine pregnancy test will be performed and evaluated prior to vaccination (in females of childbearing potential). If the urine pregnancy test is positive, the positive result will be confirmed with a serum pregnancy test. If the serum pregnancy test is positive, all study interventions will be discontinued.

The second p24CE and IL-12 DNA vaccination by electroporation will occur. Subjects will be observed for 30 minutes after vaccine administration to assess for immediate injection site reactions and adverse events.

Week 4 + 1 Day: Subjects will be contacted by telephone to check on symptoms and overall response to the injections.

10.5 p24CE, p55^{gag} and IL-12 DNA vaccinations (Stage 2)

Week 12: Routine safety studies will be performed. Plasma HIV RNA levels and CD4+/CD8+ T cell counts will be measured.

Plasma and PBMCs will be collected and cryopreserved.

A urine pregnancy test will be performed and evaluated prior to vaccination (in females of childbearing potential). If the urine pregnancy test is positive, the positive result will be confirmed with a serum pregnancy test. If the serum pregnancy test is positive, all study interventions will be discontinued.

The third DNA vaccination (p24CE, p55^{gag} and IL-12 DNA plasmids) by electroporation will occur. Subjects will be observed for 30 minutes after vaccine administration to assess for immediate injection site reactions and adverse events.

10.6 MVA vaccination (Stage 3)

Week 20: Routine safety studies will be performed. Plasma HIV RNA levels and CD4+/CD8+ T cell counts will be measured.

Plasma and PBMCs will be collected and cryopreserved.

A urine pregnancy test will be performed and evaluated prior to MVA administration (in females of childbearing potential). If the urine pregnancy test is positive, the positive result will be confirmed with a serum pregnancy test. If the serum pregnancy test is positive, all study interventions will be discontinued.

The MVA boost will be given by intramuscular injection. Subjects will be observed for 30 minutes after vaccine administration to assess for immediate injection site reactions and adverse events.

Week 20+1: Subjects will be contacted by telephone to check on symptoms and overall response to the injection.

Week 22: Routine safety studies will be performed. Plasma HIV RNA levels and CD4+/CD8+ T cell counts will be measured.

Plasma and PBMCs will be collected and cryopreserved.

A PAXgene specimen will be collected.

10.7 Combination bNAbs and lefitolimod administrations (Stage 4)

Week 24: Routine safety studies will be performed. Plasma HIV RNA levels and CD4+/CD8+ T cell counts will be measured. Samples will be stored to assess the impact of DNA/MVA prime-boost regimen on peak effector HIV-specific T cells, the primary immunologic outcome measurement.

Plasma and PBMCs will be collected and cryopreserved. Serum will be collected. A PAXgene specimen will be collected.

A urine pregnancy test will be performed and evaluated prior to bNAb infusion (in females of childbearing potential). If the urine pregnancy test is positive, the positive result will be confirmed with a serum pregnancy test. If the serum pregnancy test is positive, all study interventions will be discontinued.

The first dose of combination bNAbs will be administered. Subjects will be observed for 4 hours after bNAb administration to assess for immediate adverse events.

Week 24+1: Subjects will be contacted by telephone to check on symptoms and overall response to the combination bNAbs infusion.

Week 25-33: Lefitolimod (TLR9 agonist) will be administered subcutaneously weekly beginning one week (+/-3 days) after the bNAbs are administered and ending one week before the ATI. Following the initial dose at Week 25, the weekly lefitolimod doses may be administered on any day of the week provided the doses are at least 5 days apart. A total of 9 doses will be administered during this period.

Note: As of Protocol version 2.2 (Version Date 9/21/21) no further lefitolimod will be administered. See Appendix E. Participants who already received lefitolimod will continue with monitoring as below.

Routine safety monitoring studies will be performed at weeks 24, 26, 28, 30, and 32.

Plasma HIV RNA levels and CD4+/CD8+ T cell counts will also be measured at weeks 24, 28, 30, and 32.

Plasma and PBMCs will be collected and cryopreserved as outlined in Section 10.12.

Among women of childbearing potential, urine pregnancy test will be performed and evaluated prior to the first dose of lefitolimod (Week 24) then every two weeks (Weeks 26, 28, 30 and 32). If the urine pregnancy test is positive, the positive result will be confirmed with a serum pregnancy test. If the serum pregnancy test is positive, all study interventions will be discontinued.

Participants will be asked about the development of new ophthalmologic symptoms at every visit.

10.8 Combination bNAbs and treatment interruption phase (Stage 5)

Week 34:

Staggered Entry into Week 34 (Protocol Version 2.2)

Participants due to enter Stage 5 will have liver function tests checked within 2 weeks prior to their Week 34 visit. If ALT, AST, and total bilirubin meet criteria for grade 1 or higher (AST or ALT 1.25 x upper limit of normal (ULN), total bilirubin 1.1 x ULN), LFTs will be repeated approximately every 1-2 weeks. The team will only proceed with the second bNAb dose and ATI if/once AST, ALT, and total bilirubin are below the grade 1 threshold.

A study physician will perform a targeted hepatobiliary review of symptoms and exam in all participants on the day of and prior to administration of bNAbs. The study team will review all concomitant medications and counsel participants to discontinue any potentially hepatotoxic agents for the duration of the study.

Participants will be staggered for Stage 5 (bNAbs/ATI) entry. One participant will enter Stage 5 initially, with LFTs checked at weeks 1 and 2 following bNAbs/ATI. If these LFTs remain below the grade 1 threshold, two more participants will enter Stage 5 and have LFTs checked 1 and 2 weeks after bNAbs/ATI. If these LFTs remain below the grade 1 threshold, the remaining 2 participants will enter Stage 5.

Study Procedures

Provided that most recent HIV RNA level was below the level of quantification, subjects will take the last dose of antiretroviral drugs on the day before arriving to the clinic for the Week 34 visit. LFTs will also be checked on the day of the bNAb visit, prior to bNAb administration, to obtain a pre-bNAb/ATI baseline measure.

A second infusion of combination bNAbs will be administered at the time ART is discontinued. Subjects will be observed for 4 hours after bNAb administration to assess for immediate adverse events.

A urine or pregnancy test will be performed and evaluated in females of childbearing potential. If the urine pregnancy test is positive, the positive result will be confirmed with a serum pregnancy test. If the serum pregnancy test is positive, the subject will continue ART.

Hematology, plasma HIV RNA levels and CD4+/CD8+ T cell counts will be measured.

Plasma and PBMCs will be collected and cryopreserved. Serum will be collected.

A PAXgene specimen will be collected.

Week 34+1: Subjects will be contacted by telephone to check on symptoms and overall response to the combination bNAbs infusion.

Weeks 34 to 86 (ATI period): Subjects will be evaluated in the clinic or via a home/work RN visit weekly during the interruption period. Plasma HIV RNA levels will be measured at each visit; it is expected that the results will be available within about 4 business days.

Routine safety studies will be performed every four weeks. CD4+/CD8+ T cell counts will be measured every two weeks. In all participants, the LFT monitoring frequency will be increased to every week for four weeks, then every 2 weeks from Week 38 to Week 42, followed by monthly monitoring.

If any grade 1 or higher LFT elevation is detected, the LFTs will be repeated to confirm resolution (return to below grade 1 threshold) before additional participants enter Stage 5. If any grade 2 or higher LFT elevation is detected, further entry into Stage 5 will be halted and a review conducted by the SMC.

Plasma and PBMCs will be collected and cryopreserved as outlined in Section 10.12. Serum will be collected at the week 58 visit. Note that in cases in which clinical laboratory testing does not occur at the study site (for example, plasma HIV RNA testing arranged locally for someone living outside San Francisco), storage of specimens may be deferred.

A urine pregnancy test will be performed and evaluated every four weeks during the ATI (in females of childbearing potential). If the urine pregnancy test is positive, the positive result will be confirmed with a serum pregnancy test. If the serum pregnancy test is positive, ART will be resumed immediately.

A PAX Gene specimen will be collected at W38, W42, and W54.

Between week 46 and week 50, a routine eye exam will be repeated by an ophthalmologist.

Participants will be asked about the development of new ophthalmologic symptoms at every visit and referred to an ophthalmologist to evaluate new symptoms of any grade.

10.9 ART resumption phase (Stage 6)

Viral load criteria. Based on this rationale, we propose that treatment be initiated for any one of the following outcomes: (1) viremia > 50,000 copies RNA/mL for four weeks, (2) viremia > 10,000 copies RNA/mL for 6 weeks, (3) viremia > 2000 copies RNA/ml for 12 weeks or (4) viremia > 400 copies/RNA for 24 weeks. Operationally, this will allow for an acute viremic state that will need to resolve within 12 weeks, with high-level viremia only being allowed for a brief period. Post-treatment control (defined as viremia <400 copies RNA/mL) should be achieved prior to Week 24 post-virus rebound.

For any initial viral load greater than 400 copies/mL, we will bring individuals back immediately (within 3 working days or as soon as they are available) for a repeat test.

CD4+ T cell criteria. ART will also be reinitiated if the CD4+ T cell count declines to below 350 cells/μL on two consecutive visits. If an individual demonstrates a CD4+ T cell count <350 cells/uL, we will bring them back immediately (within 3 working days or as soon as they are available) for a repeat test.

Clinical criteria. ART will also be re-initiated for any symptoms suggestive of a severe acute retroviral syndrome, particularly signs of altered mental status or viral meningitis (severe headache, neck stiffness), but including unexplained rash, lymphadenopathy, and fevers. ART will also be re-initiated at the request of the study participant and/or her primary health care provider.

Post-ART monitoring. Once ART is reinitiated, subjects will be evaluated at Weeks 4 and 8 on ART. If viral load is not below the level of quantification by Week 8, participants will be evaluated every four weeks until the viral load is confirmed to less than the level of quantification. A follow up visit will occur 24 weeks after resumption of ART.

Routine safety studies, CD4+/CD8+ T cell counts and viral load will be performed at Weeks 4, 8, 24 and at any visits required between Week 8 and Week 24 to evaluate decrease of viral load to below level of quantification. Plasma and PBMCs will be collected and cryopreserved at the time of ART resumption and at Weeks 4, 8 and 24 on ART.

10.10 End of study

Week 86: Subjects who receive study products through week 34 will be followed through 86. Should subjects initiate ART late in the follow-up phase, the last visit might be extended. Routine safety studies will be performed every four weeks during ART. CD4+/CD8+ T cell counts will be measured every four weeks. Plasma and PBMCs will be collected and cryopreserved at the end of the study.

Given the potential for delay immune-mediated adverse events, we will collect, analyze and report all data related to any medically attended adverse events (MAAEs), including potentially immune-mediated medical conditions (PIMMCs, Appendix A). All participants will be followed for 52 weeks after their last exposure to an experimental immunotherapy (Week 86, which is 53 weeks after the last dose lefitolimod and 52 weeks after the last dose of the bNAbs). Following the updates to Protocol Version 2.2 and the withholding of lefitolimod for some participants, Week 86 will no longer be 53 weeks following the last dose of lefitolimod for all enrolled participants.

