| | 
curative study will need to enhance such responses. A common approach to enhance these responses is to co-administer an immunomodulatory (such as TLR9 agonist) with bNABs, hence generating a potent NK cell response and the capacity for ADCC.
 |
| STUDY DESIGN | 
A single arm study of twenty HIV-infected adults on effective ART will be performed.
 
All subjects will receive a combination regimen administered during ART and during an analytic treatment interruption. Our strategy has five stages; (1) IL-12 adjuvanted p24CE DNA prime (p24CE/IL-12) at Weeks 0 and 4, (2) IL-12 adjuvanted DNA boost (p24CE plus p55gag) at Week 12, (3) MVA/HIV62B (MVA62B) boost at Week 20, (4) single dose of two bNABs (VRC07-523LS and 10-1074, which target CD4 binding site and V3 loop, respectively) at week 24 with a TLR9 agonist (lefitolimod) administered weekly between Weeks 25 and 33 (9 doses), (5) ATI with single dose of VRC07 and 10-1074 at Week 34 with follow-up off ART through at least Week 46 (expected) and on or off ART (depending on outcome) through Week 86.
 
Stage 1: Subjects will first be vaccinated with IL-12 adjuvanted HIV DNA vaccines expressing 7 unique conserved elements (CE) from p24 (gag). HIV vaccine and IL-12 DNA will be administered by electroporation at Weeks 0 and 4. The goal is to generate responses to conserved regions while avoiding induction or expansion of immunodominant responses to more variable regions.
 
Stage 2: These responses will then be boosted with IL-12 adjuvanted DNA vaccine containing p24CE and full-length gag (p55) at Week 12. This strategy is expected to boost CE-specific T cell response magnitude and breadth.
 
Stage 3: Subjects will receive an MVA boost at Week 20; this vaccine is expected to further boost the CD8+ T cell responses.
 
Stage 4: A single dose of two bNABs (VRC07-523LS and 10-1074) will be administered intravenously at Week 24, with therapeutic levels expected to persist through at least Weeks 32-34. Starting at Week 25 and continuing through Week 33, subjects will receive a series of a TLR9 agonist (lefitolimod), administered weekly by subcutaneous injection. This stage has three goals: to enhance DNA/MVA vaccine responses, to generate potent NK cell responses and to reverse latency (which will allow vaccine-induced T cells and bNABs to reduce the reservoir size).
 
Stage 5: Subjects will discontinue ART at Week 34. An additional dose of the bNABs will be administered on two days prior to treatment interruption. Therapeutic bNAB levels (and continued viral suppression) are expected through at least Week 42. The goal of this
 |

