| | 
28. Individuals in whom a skin-fold measurement of the cutaneous and subcutaneous tissue for eligible injection sites exceeds 40 mm.
 
29. History of severe allergic reactions (e.g., angioedema, anaphylaxis) or severe reactions to prior vaccination (e.g., severe injection site reaction, anaphylaxis).
 
30. Chronic or active neurologic disorder which, in the opinion of the investigator, would place the participant at risk of harm or injury. Note that individuals with stable headaches, stable peripheral neuropathy, and stable post-herpetic neuralgia may be included.
 
31. Confirmed syncopal episode determined or suspected to be of cardiac origin within 12 months of screening.
 
32. Significant or progressive ophthalmologic disease, including significant signs or symptoms of active disease.
 |
| TEST PRODUCT, DOSE, AND ROUTE OF ADMINISTRATION | 
 • HIV DNA vaccine (p24CE and p55gag) plasmids • IL-12 DNA plasmid • MVA/HIV62B (MVA62B) vaccine • TLR9 agonist (lefitolimod, MGN1703) • bNAb (VRC07-523LS and 10-1074) |
| DURATION OF SUBJECT PARTICIPATION AND DURATION OF STUDY | Subjects will be observed on study for up to 112 weeks. |
| CONCOMITANT MEDICATIONS | All subjects should be maintained on a stable antiretroviral drug regimen through the end of Stage 4 and then interrupt therapy. |
| PRIMARY ENDPOINTS | 
 • Proportion of individuals experiencing a grade 3 or greater adverse event, including signs/symptoms, lab toxicity, or clinical event, that is definitely, probably, or possibly related to the study treatment. • Proportion of treated individuals who achieve post-treatment control (PTC) of viral load, defined as having an undetectable viral load (<50 copies RNA/mL) at 24 weeks after initial rebound in viremia for those who rebound or through week 24 of the interruption for those who do not exhibit a rebound |
| SECONDARY ENDPOINTS | 
 • Number of unsolicited adverse events within 28 days after administration of each study agent. • Number of any severe adverse event, medically attended adverse event, or potentially immune-mediated medical |

| | |
|-----------------------------|---|

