4 STUDY DESIGN

4.1 Study Overview

We will perform an open-label, single-arm proof-of-concept study of a four-stage curative intervention in 20 HIV-infected adults for whom ART was initiated during early (n=15) or chronic (n=5) infection. All subjects will receive the same regimen and interrupt ART.

- Stage 1 (DNA prime): Subjects will first be vaccinated with HIV DNA vaccines expressing 7 unique conserved elements (CE) from p24^{Gag} at Weeks 0 and 4. An IL-12 DNA plasmid will be co-administered with the HIV DNA plasmids. DNA will be administered with electroporation.
- Stage 2 (DNA boost): These responses will then be boosted by a combination of DNA vaccines containing p24CE and full-length gag (p55) at Week 12. An IL-12 DNA plasmid will be co-administered with two HIV DNA plasmids. DNA will be administered by electroporation.
- Stage 3 (MVA boost): Subjects will receive an MVA boost at Week 20.
- Stage 4: A combination of two bNAbs (10-1074 and VRC07-523LS) will be administered at Week 24, with therapeutic levels expected to persist through Weeks 32 to 34. Starting at Week 25 and continuing through Week 33 (10 weeks), subjects will receive a weekly dose of lefitolimod. Note: As of Protocol Version 2.2, no further lefitolimod will be administered.
- Stage 5: An additional dose of the bNAbs will be administered at two days prior to Week 34. ART will be interrupted at Week 34.

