15.4 Primary Efficacy Endpoint: Post-treatment Control

All subjects will undergo a treatment interruption designed to evaluate the primary outcome of “post-treatment control” (PTC), using the definition we recently used as part of the CHAMP Cohort collaboration¹³². In this study, PTCs were defined as individuals who remained off ART for ≥ 24 weeks and maintained viral loads ≤ 400 copies/mL for at least 2/3 of the time points. Viral loads > 400 HIV-1 RNA copies/mL were acceptable if the participant was subsequently able to suppress the viral load back to ≤ 400 HIV-1 RNA copies/mL and maintained virologic control for 24 weeks.

In our protocol, a combination of two bNAbs will be administered at the time ART is interrupted, and will likely have a persistent antiviral effect until levels wane to subtherapeutic levels, which we will assume to occur at about Week 12 of the ATI period. Also, we expect that in the post-ART and post-bNAb phase of the ATI that a period of acute viremia will occur, and that this could last for up several weeks. As described in Section 1.11, ART will be initiated if plasma HIV RNA levels remain consistently $> 50,000$ copies RNA/mL for four weeks, $> 10,000$ copies RNA/mL for six weeks, > 2000 copies RNA/mL for $>$

12 weeks, and > 400 copies RNA/mL > 24 weeks. In this scenario, post-treatment control will only be achieved once viremia falls below 400 copies RNA/mL and remains there for 24 weeks.

Success will hence be defined in two ways. First, subjects who fail to show any consistent rebound above 400 copies RNA/mL between Week 12 of the ATI (when bNAbs levels wane) and Week 36 of the ATI will be considered as having achieved post-treatment control. Second, subjects who exhibit a rebound and eventually achieve 24 weeks of virus control will be considered as having achieved post-treatment control.

Failure will be defined based on the need to resume ART due to high-level viremia, dropping CD4+ T cell counts, or clinical events (see Section 1.11).

The proportion of individuals who achieve our study-defined PTC will be the primary outcome.

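### Under the Section 15.4 definition, follow-up to Week 86 is too short to classify slow post-treatment controllers, and the plan has no rule for counting them

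*Combined protocol and SAP*

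**What the plan says.** **Timing.** Section 4.1: "ART will be interrupted at Week 34". Section 10.8 labels the interruption "Weeks 34 to 86 (ATI period): Subjects will be evaluated in the clinic", and the synopsis describes follow-up "on or off ART (depending on outcome) through Week 86". Section 10.10: "Subjects who receive study products through week 34 will be followed through 86". The extended-ATI table in Section 10.12 has its last off-ART viral load at Week 86, with a window of plus or minus 2 weeks on the End Study visit. The one extension described in Section 10.10 concerns late restart: "Should subjects initiate ART late in the follow-up phase, the last visit might be extended".

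**Endpoint.** Section 15.4 gives two routes to success. Route 1 is no consistent rebound above 400 copies/mL between ATI weeks 12 and 36. Route 2: "subjects who exhibit a rebound and eventually achieve 24 weeks of virus control will be considered as having achieved post-treatment control". The same section specifies 400 copies/mL as the level for that control, assumes that the antibodies wane at about ATI week 12, and defines failure by the need to resume ART.

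**Permitted viremia.** The last of the four viral-load restart criteria in Section 10.9 is "viremia > 400 copies/RNA for 24 weeks". That section also expects the acute viremic phase to be over within 12 weeks.

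**Passages that point past Week 86.** The synopsis states: "Subjects will be observed on study for up to 112 weeks". The text that closes Section 10.12 describes two-weekly visits after the first 24 weeks of the ATI without a stop date, and a table footnote says that the End Study visit is not the study's final visit.

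**The concern.** Route 2 needs a viremic phase followed by 24 weeks of control, and both must fit inside the observed interruption. The restart criteria tolerate low-level viremia for so long that, after a rebound at the expected time, the two together can outlast the 52 weeks scheduled. A participant who is controlled and off ART at Week 86 but short of 24 weeks has not met route 2. Nor has that participant needed ART, so the failure definition is not met either.

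This is the primary efficacy endpoint. It is judged on 15 early-ART participants with a cut-off of 6, so the handling of one or two people can decide the result. Counting them as non-PTC biases the proportion downward. Settling the question after the results are known leaves the choice open to influence.

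**Working it through.** **The plan's own figures (Section 15.6).** With n = 15 and a null rate of 15%, P(X ≥ 6) = 0.017 by exact binomial. The likelihood ratio test named in the synopsis gives P = 0.019 for 6/15 and 0.077 for 5/15, so the cut-off of 6 is right. Power at 47% is P(X ≥ 6 | 15, 0.47) = 0.788, against a stated 80% or more. It is 0.799 at 47.5% and 0.810 at 48%, so the stated power is reproduced to within about one point.

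**Time available.**
- Observed ATI: 86 − 34 = 52 weeks.
- Latest start of control for route 2: 52 − 24 = ATI week 28, which is Week 34 + 28 = 62.
- Using the full 2-week window: 54 − 24 = ATI week 30.

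**Time needed.** Finish = rebound week R + weeks of viremia V + 24. Section 15.4 puts antibody waning at ATI week 12. The synopsis expects rebound some weeks after that, so 16 is shown as well (my allowance). The synopsis also expects therapeutic levels to at least Week 42, which is ATI week 42 − 34 = 8.

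| R (ATI week) | V (weeks) | Finish (ATI week) | Study week | Against ATI week 52 |
|---|---|---|---|---|
| 12 | 12 | 48 | 82 | 4 to spare |
| 16 | 12 | 52 | 86 | fits, no margin |
| 12 | 16 | 52 | 86 | fits, no margin |
| 8 | 24 | 56 | 90 | 4 short |
| 12 | 24 | 60 | 94 | 8 short |

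After a rebound at ATI week 12, up to 16 weeks of viremia can be accommodated. The full 24 weeks fits only if rebound occurs by ATI week 52 − 24 − 24 = 4. The visit window does not rescue the last row: 60 − 54 = 6 weeks are still missing.

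**The gap between the routes.** A consistent rebound at ATI week 29 to 35 falls inside the route 1 period (12 to 36), so route 1 fails. Control cannot start before ATI week 29, so 24 weeks finish at ATI week 53 or later, after the Week 86 visit. Only an almost immediate return to control at ATI week 29 or 30 could be caught by the window. A participant whose first rebound is at ATI week 37 has already succeeded by route 1.

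**Effect on power (illustration; the documents give no rate).** Suppose a fraction f of true controllers is not counted. The observable rate is then 0.47 × (1 − f), and power is P(X ≥ 6 | 15, that rate):
- f = 0: rate 0.470, power 0.788
- f = 0.10: rate 0.423, power 0.666
- f = 0.20: rate 0.376, power 0.521

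**The case against.** **The expected course fits.** Section 10.9 anticipates viremia resolving within 12 weeks, and Section 1.11 says four to 12. A reader might infer that the trial cannot see the very controllers it is meant to reveal. The documents do not support that: only the slow tail is lost.

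**Week 86 may not be a hard stop.** A reader might conclude that slow controllers can never be classified. The closing text of Section 10.12, the End Study footnote and the 112-week maximum all leave room for later visits, and Section 10.10 explains Week 86 as a 52-week safety horizon. This stands in part: the document contradicts itself rather than settling on an impossibility. But no off-ART viral load is scheduled after Week 86, and the extension in Section 10.10 is tied to late ART restart.

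**The synopsis endpoint is shorter.** It asks for fewer than 50 copies/mL at 24 weeks after rebound. A rebound at ATI week 12 is then assessed at 12 + 24 = ATI week 36, and only rebounds after ATI week 28 fall outside. So the 8-week shortfall depends on Section 15.4. That is correct, and it adds a conflict to resolve.

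**A larger shortfall.** A reader might take waning at 12 to 16 weeks from Section 1.3 and reach 16 + 24 + 24 = ATI week 64, 12 weeks short. Section 1.3 gives that range for VRC07-523LS only, with formal pharmacokinetic analysis pending, and gives at least 8 weeks for 10-1074. A delay between waning and rebound would add to the 8 weeks one for one, but the documents put no figure on it.

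**Intention-to-treat implies a default.** Section 15.1 includes everyone who starts therapy, and the outcome is the proportion who achieve PTC, so an undetermined participant would naturally be non-PTC. That is conservative against the 15% null. It remains an inference, and it does not remove the downward bias.

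**A larger loss of power.** Dropping two or three of the 15 gives P(X ≥ 6 | 13, 0.47) = 0.630 or P(X ≥ 6 | 12, 0.47) = 0.530. Those figures remove participants whatever their outcome, whereas the people affected here are controllers, and no document supports a count of two or three.

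**Conclusion.** The point holds for late courses under Section 15.4. Route 2 can be observed by Week 86 only if control starts by ATI week 28. The expected course meets this, with a margin of 0 to 4 weeks. Rebound at ATI week 12 with more than 16 weeks above 400 copies/mL does not, and at the limit that Section 10.9 permits it is 8 weeks short. A consistent rebound at about ATI week 29 to 35 can, in practice, satisfy neither route. If such participants are controlled and off ART at Week 86, Section 15.4 leaves them unclassified.

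The conclusion assumes the Section 15.4 endpoint, waning at about ATI week 12, and no off-ART viral load after the visits listed in Section 10.12. The number affected is unknown, so the fall in power from 79% to 67% or 52% only illustrates sensitivity. This should be fixed, but it does not undermine the design.

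**What to change.** 1. Reconcile Section 10.10 and the Section 10.12 table (Week 86) with the closing text of Section 10.12 (two-weekly, no stop date), the synopsis (its PTC endpoint and the 112 weeks) and Section 15.4.
2. For participants who remain off ART at Week 86 under the existing rules with PTC status undetermined, continue plasma HIV RNA at the existing two-weekly frequency until 24 weeks of control are complete or ART is restarted. This concerns observation only. The restart criteria stay as they are, and time off ART remains the sponsor's decision.
3. State in Section 15.4 that anyone still undetermined is non-PTC in the primary analysis. Add a sensitivity analysis that counts those below 400 copies/mL at their last visit as PTC.

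**Cost.** A protocol amendment and a few extra viral-load visits for those still off ART and undetermined. The 112-week maximum needs checking, because the 24-week visit after ART restart exceeds it for any restart after Week 88 (88 + 24 = 112). A restart at Week 94, for example, would run to Week 118.
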